### 8.3 Definitions relevant to the classification of adverse events

Severity (serious/not serious), also called seriousness (serious/not serious). It is defined as serious or grave. any event that: results in death, threatens life, requires hospitalization or prolongs the hospitalization, are a cause of permanent or significant disability or incapacity, are a cause of alterations or malformations in the newborn, other medically important conditions.

Severity (mild, moderate, or severe). Mild symptoms are those that occur with minimal symptoms, not require treatment or discontinuation of the medication; moderate, when they interfere with activities Common, non-life-threatening conditions require treatment and may or may not require discontinuation of the medication; severe, those that interfere with normal activities and require treatment pharmacological and discontinuation of the medication.

Causality. It is the relationship assigned between the medication and the adverse event: certainly caused by the drug, there is clear evidence of causality, ie the adverse event reappears with administration of the drug; probably caused by the drug, there is a high suspicion of causality but There is no direct evidence or it is considered unnecessary or dangerous, ie the reaction disappears when discontinue the medication; possibly caused by the medication, there is additional information that suggests that the cause may be due to another medication or disease; unlikely to be caused by the medication, there is a clear explanation of the origin due to the underlying disease or the use of another medication; conditional, data are lacking to issue a clear causality; not classifiable, those for which Once all possible information has been obtained about the adverse event, it remains unclassifiable.

#### 8.4 Researcher Responsibilities

It is the Researcher's responsibility to perform the EA verification through questioning, reviewing the information recorded in the subject's diary, the relevant physical examination, the evaluation of progress, as well as such as appropriate medical and pharmacological management; as well as follow-up until resolution or outcome and final discharge of the EA, following the definitions determined in national and international regulations. [48] [49] [50]

In the event of an AE or any event that puts the health and well-being of the Subjects will be provided with relevant medical care either at the research center or will be referred to the Hospital Center with the greatest resolution power with which the research center has an agreement medical attention. The IP will notify the sponsor's clinical monitor, according to the times established in the national and international regulations. In the case of serious adverse events, the sponsor will be notified and will record the corresponding information in the eCRF and, in turn, will inform the CEI and the CI.

The attention of the EA will be carried out according to the event attention diagram (see **Figure 3. Attention of the adverse event**).

In the final report that will be written by the Clinical Team of the Department of Clinical Operations of Laboratories Sophia, SA de CV, the report of adverse events will be included in compliance with national and international regulations. current international. [49] [48]

If the research subject debuts during his/her participation in the study with any adverse event of chronic course, such as diabetes or systemic arterial hypertension, you will be referred to a health professional. competent health for your chronic treatment. The follow-up and completion of your participation will be as stipulated by the ICH.

#### 8.4.1 Recording of adverse events in the electronic case report form

The EA registry considers:

- The subject's identification information such as: code, age, sex, left eye, right eye.
- Information about the type of AE to the PI or the study drug, as appropriate.
- Information on important dates:
  - o Date on which the EA occurs
  - o Date on which the IP is informed of the same
  - o Date of resolution or outcome, as applicable.
- Information on diagnosis and clinical management. If a lack of therapeutic response to the PI and/or investigational drug, must be reported as a serious adverse event within the period stipulated by current regulations. Include the therapy used in concomitant medications for the pharmacological management of the adverse event.
- Establish the outcome or resolution of the event:
  - o Patient recovered without sequelae
  - o Recovered patient with sequelae
  - o Patient not recovered
  - o Patient who died due to AE
  - o Patient who died and it is judged that the drug may have contributed
  - o Patient who died and this was not related to the product or medication in question investigation,

Or, indicate that the consequence of the event is unknown.
- Information about the investigational product or drug or the drug associated with the EA, RAM or SRAM. As applicable, information concerning generic name, distinctive name or code of the PI and/or investigational medicinal product, as appropriate according to the methodological design of the study, this is relevant in the case of blinded studies or those where placebo is used as comparators, since there are circumstances that justify opening the blind to determine whether the adverse event may be attributable to the active agent, the combination of active agents, or the substance(s) pharmacologically inert(s), such as vehicles or additives, as appropriate for the phase clinical research in which the development of the drug is located. It will also be necessary record the data concerning the batch number, manufacturing laboratory, expiration date, dose, route of administration, start and end dates of administration and/or consumption, reason for the prescription; depending on whether it is an investigational product or drug (protocol in which that the patient is currently participating in) or it is a medication that the subject is currently undergoing research

consumed for the treatment of underlying concomitant diseases or used for the management of any transient sign or symptom that does not correspond to the Natural History of the pathology that caused it your entry into the research protocol.

[figure not shown]
- Indicate the withdrawal or maintenance of the drug, PI or investigational drug, as appropriate.  
appropriate. Indicate whether when withdrawing the PI or investigational drug or suspected drug (if the event is caused) the adverse event disappears. Also indicate whether an adjustment is made to dose, if the event changes in intensity or severity, persistence of the reaction. It is  
It is important to indicate whether in those patients who are exposed again to the PI, medication in investigation or medication, which had previously been suspended, the AE reappears.
- Information regarding concomitant pharmacotherapy. Indicate the generic name, the dose, route of administration, start and end dates of use, as well as the reason for the prescription regardless of whether it is in accordance with the prescribing information or technical data sheet or is used outside of the regulations or what has been authorized by the local, national or regulatory entity international.
- Information on relevant clinical history. The analysis of the AE considers the information previously narrated, notwithstanding the clinical context in which said harmful phenomenon occurs in the participants of the clinical research protocol, is of special interest, so the information about previous conditions, hypersensitivity or allergy phenomena, previous surgical procedures, laboratory tests or office examinations that have been performed performed on the participant, etc., that the researcher deems appropriate to mention may do so.

#### 8.4.2 Monitoring of adverse events

The IP will provide care and guidance for the EA presented by the participant until its outcome, according to what is referred to in the following section.

### 8.4.3 Procedures for a serious adverse event

The EA care process considers the following stages:

**Figure 3. Adverse event care**

During the development and conduction of this study, events may occur in the subject under investigation.

harmful undesirable or adverse reactions, of medical implication, which do not necessarily have a causal relationship with the PI or investigational drug. These harmful phenomena may occur during the use of investigational medicinal products at doses authorized for use in humans, by a local, national or international regulatory body. However, there may be a suspicion that the IP or the investigational drug may cause any undesirable clinical manifestation. The AEs, ADRs or SRAs to one or several medications may occur during the systematic evaluation of participants (on days in that the clinical review is scheduled, according to the schedule of activities) or suddenly, in such a way that:

1. The researcher must be the first person to whom the patient notifies that he or she has developed or presented with any harmful clinical phenomenon during his or her participation in the present study.
2. Based on clinical judgment, the principal investigator will determine the appropriate course of treatment for the adverse event/reaction based on the relevant physical examination, history, etc., as well as the analysis of information available in the medical literature and the information contained in the investigator's manual, Prescribing Information, or the comparator drug's data sheet.
3. Such care may be provided at the research center or at the hospital with the highest capacity for treatment. Thus, if the patient is referred by the PI to a hospital, they will receive care through a referral system. The referral may be through a card identifying the subject as a study participant and linking them to the pre-established agreement with the institution, or through a referral medical note issued by the PI. Laboratorios Sophia, SA de CV, will pay the costs for medical care for participating patients when the adverse event is associated with or related to the PI or investigational drug.
4. Taking into account the clinical information collected, either during the care provided at the research center or provided by the treating physician(s) at the hospital, the IP will record the AE in his/her clinical note, noting the seriousness, intensity (mild, moderate, or severe), and relationship with the product or drug under investigation.
5. The PI must migrate the relevant data to the eCRF and its respective adverse event section. Therefore, in cases of serious adverse events, which must be reported within 24 hours of the PI becoming aware of them, the clinical monitor of the study is informed and, in turn, informs the Clinical Team and the UFTLS, so that the IEC is subsequently informed. Regarding non-serious adverse events, these will be recorded and appropriately addressed, and the corresponding regulatory entity will be informed about the safety profile of the PI or investigational drug in the final report of the clinical trial.

The recording of the outcome of the EA depends substantially on the follow-up that the IP carries out on the subject, since

Most harmful phenomena are expected (see safety profile section in the manual)

of the researcher), are of an ophthalmic nature, however, there may be systemic alterations. Therefore,

The researcher's judgment will consider the withdrawal of the participant or his/her continuation.

#### 8.4.4 Causality Assessment

Causality assessment is the methodology used to estimate the probability of attributing to a drug, investigational drug or PI, the observed adverse event. Consider categories probabilistic according to the available evidence and the quality of the information, based on national regulations pharmacovigilance.[48]

The Pharmacovigilance and Technovigilance Unit of Sophia Laboratories (UFTLS) can use the algorithm of Karch and Lasagna modified by Naranjo referred to by Aramendi I, as a tool to facilitate the Probabilistic categorization of causality. In this algorithm, different items are scored, which, They allow a value to be assigned to the cause-effect relationship between the administration of the medication and the reaction adverse. [51] See **Table 4. Karch and Lasagna algorithm modified by Naranjo.**

In such a way that the degree of certainty to establish the PI or investigational drug (according to (as appropriate) as the causal agent of the harmful phenomenon that occurs to the subject of the clinical study.

It can also be indicated directly by the IP based on his clinical experience or through the voluntary application of the aforementioned tool. However, it is important that the researcher and the UFTLS take into account the following arguments in favor of the causal relationship:

- a) Strength of association, which refers to the number of cases in relation to those exposed.
- b) The consistency of the data, that is, the presence of a common characteristic or pattern.
- c) The exposure-effect pattern, which determines the relationship with the site of appearance, time, dose and reversibility after suppression.
- d) Biological plausibility, which refers to possible pharmacological or pathophysiological mechanisms involved in the development or presentation of the adverse event.
- e) Experimental findings, for example, the appearance of anomalous metabolites or high levels of drug or the product of its biotransformation.
- f) Analogy, which refers to the experience acquired with other related drugs, adverse reactions frequently produced by the same family of pharmacological agents.
- g) Nature and characteristics of the data, i.e. objectivity, accuracy and validity of the documentation relevant. [52]

No.	Reagent	Score	
		Yeah	No
1.	There are conclusive previous reports on adverse drug reaction, adverse event or suspected adverse reaction to medication	+1	0
2.	The adverse event occurred when the suspected drug was administered	+2	-1
3.	Adverse drug reaction, adverse event or suspected adverse drug reaction improved by discontinuing or administering a specific antagonist	+1	0
4.	Adverse drug reaction/adverse event/suspected adverse drug reaction reappeared upon administration of the investigational drug/product/investigational drug	+2	-1
5.	There are alternative causes that can provoke this reaction.	-1	+2
6.	The adverse reaction/adverse event/suspected adverse reaction to medication occurred after the placebo administration	-1	+1
7.	The drug was determined in blood or other fluids in toxic concentrations	+1	0
8.	The intensity of the adverse reaction/adverse event/suspected adverse drug reaction was higher with higher doses or lower with lower doses	+1	0
9.	The patient has had similar reactions to the investigational drug/product or medication in research, in the past	+1	0
10.	The adverse reaction/adverse event/suspected adverse reaction to medication was confirmed with some objective evidence	+1	0
Total score		summation	

Probabilistic category based on the score obtained

I	The causal relationship is verified	≥9
II	The ADR is likely due to the investigational drug or product	5 to 8
III	The ADR may be due to the investigational drug or product	1 to 4
IV	The causal relationship is doubtful	0

Each reagent receives a defined score and the final sum allows estimating the probabilistic category of the causal relationship. effect between the administration of the investigational product and the adverse reaction, adverse event, or suspected reaction adverse.

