### 4.1 Design Overview

Phase I clinical trial, controlled, non-comparative, open, single-center

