### 6.1.2 Reference product

Non-comparative study.

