## 6.3 Concomitant treatments and medications not authorized during the study

The use of concomitant medications by any route of administration will not be permitted during the intervention period. Except as specified for the study procedures and the use of Hormonal contraceptives in women of childbearing age. The purpose of this restriction is to avoid interactions pharmacological agents that could alter the results of the variables evaluated.

Permitted medications:

- Ophthalmic:
  - or Tetracaine 0.5%
  - o Tropicamide 0.8% / Phenylephrine 5%

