- ~~PI Assignment~~: Refers to determining the intervention the patient will follow during the study. Since this is an open-label study, all eligible subjects will be assigned to PRO-172. However, assignment is the procedure by which the number of a given medication is linked to the subject's identification number. This assignment will be performed at the baseline visit (day 1).
- ~~Delivery of the PI and start of intervention~~: Refers to the delivery of the PI to the study patient by the research center.

- EA Assessment: See 7.3.3.1
- Delivery of patient materials and instructions for completion: This refers to the PI providing the subject with the subject's diary, identification card, and calendar, improving adherence. Staff assigned by the research center will provide the subject with prior training on how to complete the diary.

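### The causality algorithm scores a placebo item in a trial without placebo, so every event scored with it gains an uninformative +1 and an event answered Yes on timing cannot be rated doubtful

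*Protocol*

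**What the plan says.** The trial has a single arm. Protocol 4.1 describes it as "Phase I clinical trial, controlled, non-comparative, open, single-center", 6.1.2 says "Non-comparative study", and 7.4.1.1 says "Since this is an open-label study, all eligible subjects will be assigned to PRO-172".

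Protocol 8.4.4 gives a ten-item causality algorithm (Table 4). The sponsor's pharmacovigilance unit may use it. The investigator may apply it voluntarily or assign causality from clinical experience. Each item has a Yes score and a No score only, and the note under the table says every item receives a score. Three items matter most here:

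- Item 2, "The adverse event occurred when the suspected drug was administered": Yes +2, No -1.
- Item 5, "There are alternative causes that can provoke this reaction": Yes -1, No +2.
- Item 6, "The adverse reaction/adverse event/suspected adverse reaction to medication occurred after the placebo administration": Yes -1, No +1.

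The total is read against four bands: 9 or more (I), 5 to 8 (II), 1 to 4 (III, possible product effect) and 0 (IV, doubtful). Negative totals have no band.

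Protocol 8.3 has a separate six-level causality scale. Its unlikely level applies when "there is a clear explanation of the origin due to the underlying disease or the use of another medication". The SAP table of variable definitions (6.2) codes causality in two levels: probably or possibly related, and unlikely related.

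**The concern.** An item about placebo has nothing to measure when nobody receives placebo. Because No earns +1 and not 0, the item adds a point towards causation to every event scored with the tool. That point is enough to close the lowest category to any event whose timing item is answered Yes.

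The result feeds the primary endpoint. Relatedness is one of the two conditions for an event to count (the other is that it is unexpected), and Protocol 10.1.5 calls the product safe and tolerable when fewer than 10% of subjects have such an event. An event with another cause could be unlikely by 8.3 and category III by Table 4. Neither document says which result enters the endpoint, or how the six levels of 8.3 and the four of Table 4 map to the SAP's two.

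**Working it through.** The plan states no figure to reproduce; the check is a count over the printed scores in Table 4.

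**Inputs (Protocol 8.4.4, Table 4)**

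| Item | Yes | No |
|---|---|---|
| 2 timing | +2 | -1 |
| 4 reappearance on administration | +2 | -1 |
| 5 alternative cause | -1 | +2 |
| 6 placebo | -1 | +1 |
| 1, 3, 7, 8, 9, 10 (each) | +1 | 0 |

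**Step 1. Lowest total when item 2 is Yes and item 6 is No.** Take item 4 = No, item 5 = Yes and the six remaining items = No:

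+2 - 1 - 1 + 1 + 0 = 1, category III.

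The other eight items give 2^8 = 256 answer patterns. Their totals run from 1 to 13, and none is 0 or below.

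**Step 2. The same event with item 6 at 0.**

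+2 - 1 - 1 + 0 + 0 = 0, category IV.

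**Step 3. All 256 patterns with item 2 = Yes.**

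| Item 6 score | I | II | III | IV |
|---|---|---|---|---|
| +1 | 71 | 141 | 44 | 0 |
| 0 | 44 | 141 | 70 | 1 |

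Totals of 9, 5 and 1 each drop one category. These are counts of patterns, not probabilities of events.

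**Step 4. Dependence on item 4.** If item 4 were also scored 0, as untested, the minimum with item 6 at 0 would be +2 + 0 - 1 + 0 = 1, again category III. The correction therefore opens category IV only if item 4 keeps its -1. That is reasonable here: dosing four times a day for 7 days (Protocol 6.1.3) gives up to 4 x 7 = 28 applications, so an event that occurs once and does not return under continued dosing can be answered No on evidence.

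**Step 5. Item 2 answered No.** With items 4 and 6 at No and item 5 at Yes:

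-1 - 1 - 1 + 1 = -2.

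Of these 256 patterns, 22 total 0 or below. Table 4 has no band for a negative total.

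**Step 6. Link to the decision rule.** With 22 subjects analysed, 2/22 = 9.1% passes and 3/22 = 13.6% fails. The boundary lies between two and three subjects.

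**The case against.** The case for leaving this alone is substantial, and most of it stands.

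- **The tool is optional.** Nothing gives a Table 4 total precedence over 8.3, and the investigator can already code an event unlikely by judgement. This limits the effect to events scored with the tool. It does not settle which result counts when the two routes disagree.
- **Not every event after a dose is affected.** A reader might infer that no post-dose event can score below category III. That fails when item 2 is answered No (step 5), as it could be for an event after the last drop.
- **Diagnostic drops are not a firm example.** A reader might infer that effects of the anaesthetic, the dyes or the optional mydriatic will be charged to PRO-172. In 7.4.1.1 the stains and the eye examination are listed, in suggested order, before the product is assigned and delivered. The day 8 visit follows the 7 dosing days. Item 2 can defensibly be No at both times.
- **8.3 and Table 4 do not always disagree.** The 8.3 definition of possible also covers events where other information points to another drug or disease. The two scales conflict only when the other explanation is clear.
- **Correcting item 6 moves little.** One pattern in 256 reaches category IV. The shifts from I to II and from II to III would probably stay on the related side of the SAP code. The +2 on item 2 contributes more to the floor than item 6 does.
- **The bias is cautious.** It runs against the product, in the first human study of this formulation.

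What remains is a scoring rule that is wrong as printed. The pattern it affects is plausible for this endpoint: an unexpected event with another cause, no recurrence under repeated dosing, no drug level measured and no dose change.

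**Conclusion.** The point holds in limited form. Item 6 adds an uninformative +1 to every event scored with Table 4. If item 2 is Yes, that raises the minimum total from 0 to 1, so category IV cannot be reached even when another cause is present, while 8.3 permits unlikely for a clear other explanation.

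This rests on three conditions: the tool is used, item 2 is answered Yes, and item 4 is scored No with its -1. That category III would count as related in the SAP's two-level code is a natural reading, but the documents do not state it.

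The documents do not support a claim that the trial's verdict will change. That would take exactly two other subjects with qualifying events, plus one event scored with the tool on the affected pattern. The step from 9.1% to 13.6% shows how little room the rule leaves; it does not measure this defect. The correction is worth making because it costs almost nothing and the category can decide whether an event counts.

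**What to change.** In Protocol 8.4.4:

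1. Score item 6 as 0 for all subjects, because no placebo is given.
2. Class totals of 0 or below as category IV, so that negative totals have a place.
3. State before analysis whether 8.3 or Table 4 supplies related for the primary endpoint, and how each of its categories maps to the SAP's two-level causality code. Carry the same mapping into the SAP variable table, so that Protocol 8.3, Protocol 8.4.4 and the SAP agree.

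A further step would be to let an unlikely rating under 8.3 override any Table 4 total. I would not add it: in an open safety study it widens the discretion to discount events, and item 3 already settles which scale governs.

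The cost is a few sentences in the protocol and a short mapping in the SAP. The drawback is that the algorithm would no longer be used exactly as printed, which the final report should state.
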